Subjects who prematurely discontinue the study treatment (secukinumab or GP2017) are encouraged to remain in the study to continue the study-related assessments until the completion of the study at Week F120. Every effort should be made to request the subjects to complete the final X-ray evaluations as part of the Week 104 visit assessments. Please refer to [Section 5.6.2](#) for reasons for study treatment discontinuation.

Subjects who prematurely discontinue completely from the study for any reason should return for the final visit to conduct the Week 104 assessments (4 weeks after the last study treatment administration of secukinumab or 2 weeks after the last study treatment administration of GP2017), as well as return for the follow-up visits (Week F112 and F120). Every effort should be made to request discontinued subjects to complete the final X-ray and MRI evaluations as part of the Week 104 visit assessments, unless the last X-ray and/or MRI was taken within 12 weeks prior to discontinuation.

At the final visit, all dispensed investigational product should be reconciled and the adverse event and concomitant medications reconciled on the CRF.

If the subject refuses to return for these assessments or is unable to do so, every effort should be made to contact him/her or a knowledgeable informant by telephone to determine the reason. Attempts to contact the subject should be recorded in the source documentation.

Table 6-1 Assessment schedule – Part 1: Screening to Week 52

Period	Screening			Treatment																											
	SV1 -10 to -4	SV2 -4 to BSL	BSL	1	2	3	4	6	8	10	12	14	16	18	20	22	24	26	28	30	32	34	36	38	40	42	44	46	48	50	52
Optional site visit				X	X	X		X	X	X		X		X	X	X		X	X	X	X	X	X	X		X	X	X	X	X	
Obtain informed consent	X																														
Inclusion/ Exclusion criteria ¹	X	X	X																												
Relevant medical history/ current medical condition	X	X	X																												
Prior medication	X	X	X																												
High sensitivity C-reactive protein (hsCRP)	X		X																												
X-ray of SI joints ²	X ⁴																														
X-ray (cervical + thoraco- lumbar) for mSASSS ²	X ^{3,4}		X ^{3,4}																												
Local PPD skin test ⁵ or Central laboratory test for tuberculosis screening	X																														
AS disease assessment ⁶		X																													
Demography		X																													

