### 2.5.3 Handling of missing values/censoring/discontinuations

Missing Week 104 data for a given subject who discontinued in the study will be imputed using an imputation model based on the observed data of subjects in the same randomized arm who also discontinued study treatment but for whom Week 104 X-ray data are available ('retrieved dropout approach', [EMA 2010](#)) and based on the observed data of the given subject.

A logistic regression model will be fitted to the Week 104 X-ray data for the retrieved dropout patients, while adjusting for treatment, baseline mSASSS and post-baseline slope in mSASSS.

The post-baseline slope is defined as the last available post-baseline change in mSASSS score divided by study day on which the X-ray was taken. Recent literature suggests that in AS patients treated with TNF inhibitors the spinal radiographic progression followed a linear course during the first 4 years of follow-up (Maas, et. al. 2017). Thus, the linearity assumption is expected to be reasonable. The covariates of baseline mSASSS and slope will be standardized to have a mean of 0 and standard deviation of 1 before model fitting.

PROC MCMC will be used for fitting the logistic regression model and multiple imputation of the Week 104 value, with weakly informative priors and model code as shown below,

```
prior beta1 ~ normal(0,sd=2);
```

```
prior beta2 ~ normal(0,sd=2);
```

```
prior beta3 ~ normal(0,sd=2);
```

```
prior beta4 ~ normal(0,sd=3);
```

```
prior beta5 ~ normal(0,sd=3);
```

```
pi = logistic(beta1*trt_GP2017 + beta2*trt_SEC150 + beta3*trt_SEC300 +  
beta4*sqrt(base_stand) + beta5*slope_stand);
```

```
model noprog ~ binary(p = pi);
```

where trt\_GP2017 – binary indicator for GP2017 40 mg

trt\_SEC150 – secukinumab 150 mg

trt\_SEC300 – secukinumab 300 mg

sqrt(base\_stand) – square root of the baseline mSASSS (standardized)

slope\_stand – the last available post-baseline change in mSASSS score divided by study day on which the X-ray was taken (standardized)

noprog – no radiographic progression at Week 104

If all post-baseline values are missing for a subject, the subject will be imputed based on a similar model as above but just based on treatment and baseline value as covariates (without the post-baseline slope variable). Subjects with a missing baseline will be excluded from the analysis.

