Missing Week 104 data due to an incomplete number of interpretable locations for a given subject will be imputed using the same imputation model as described above but based on the observed data of all subjects who provided Week 104 data and based on the observed data of the given subject.

In this way multiple complete data sets are created and for each of these completed datasets the response rate will be calculated and then combined using Rubin's rule.

The potential sparsity of the retrieved data may preclude fitting the proposed model to impute the subjects with missing X-ray data at Week 104. In this case, a fallback approach will be utilized.

In case of low sample size of the retrieved dropout data (< 8 for any treatment group), the imputation model can lead to unstable imputations. In this case imputations will be performed based on a model without treatment as a covariate.

$$pi = \text{logistic}(\text{beta1} + \text{beta4} * \text{sqrt}(\text{base\_stand}) + \text{beta5} * \text{slope\_stand})$$

In case there are less than 8 retrieved dropout patients overall, the same imputation model as above will be used (without treatment as a covariate) but based on all patients (not only retrieved dropout patients).

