### 2.6.3 Handling of missing values/censoring/discontinuations

Missing Week 104 change from baseline values in mSASSS for a given subject will be imputed using an imputation model based on the observed data of subjects in the same randomized arm who also discontinued study treatment but for whom Week 104 X-ray data are available (‘retrieved dropout approach’, EMA 2010). Recent literature suggests that in AS patients treated with TNF inhibitors, the spinal radiographic progression followed a linear course during the first 4 years of follow-up (Maas, et. al. 2017). Therefore, a parametric model assuming a normal distribution and a linear time trend for the mean scores will be used to impute missing Week 104 values. The model will be fitted to the average of the three readers’ change from baseline in mSASSS.

We will consider a mixed-effects model for the change in mSASSS functional scale measurement. Let  $y_{ij}$  be the  $j^{\text{th}}$  change from baseline measurement of subject  $i$ , at time  $t_{ij}$ :

$$y_{ij} = \alpha_i t_{ij} + \epsilon_{ij} \text{ with } \epsilon_{ij} \sim N(0, \sigma^2).$$

The subject specific intercept  $\alpha_i$  will be modelled using treatment and the subject's baseline mSASSS value as fixed effects and assuming a subject-specific normally distributed random effect.

PROC MCMC will be used for fitting the mixed-effects model and multiple imputation of the Week 104 value, with weakly informative priors and model code as shown below,

```
random gamma ~ normal(0, sd=sd_re) subject=usubjid;
prior beta1 ~ normal(0,sd=100);
prior beta2 ~ normal(0,sd=100);
prior beta3 ~ normal(0,sd=100);
prior beta4 ~ normal(0,sd=100);
prior beta5 ~ normal(0,sd=100);
prior sd_re ~ uniform(0,20);
prior sd ~ uniform(0,20);
mu = (beta1*trt_GP2017 + beta2*trt_SEC150 + beta3*trt_SEC300 + beta4*base +
beta5*sq_base_stand + gamma)*ady/365.25;
model chg ~ normal(mu, sd=sd);
```

where trt\_GP2017 – binary indicator for GP2017 40 mg

trt\_SEC150 – binary indicator for secukinumab 150 mg

trt\_SEC300 – binary indicator for secukinumab 300 mg

base – baseline mSASSS

sq\_base\_stand – square root of baseline mSASSS (standardized)

gamma – random effect

ady – number of days when X-ray assessment was done after randomization

chg – change from baseline in mSASSS at Week 104

For absence of new syndesmophytes at Week 104, the handling of missing data will be the same as the primary endpoint.

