## 3 Sample size calculation

An overall type I error (2-sided) of 5% will be used to control type I error. A total of 279 subjects per group is deemed appropriate to achieve adequate power for the primary and secondary endpoints for this study.

Based on the modeling of data from an unpublished non-interventional study that compared a blinded re-read of radiographic x-ray images from the secukinumab phase III AS study CAIN457F2305 (MEASURE 1) (Braun 2016) and a historical cohort of AS subjects treated with NSAIDs only (ENRADAS), a no progression rate of 66% for secukinumab-treated subjects and 51% for NSAIDs-treated subjects at Week 104 were calculated. Published data for adalimumab-treated AS subjects compared to a cohort of AS subjects treated only with NSAIDs (OASIS) showed no difference in change from baseline in mSASSS at Week 104 (van der Heijde 2009). Therefore, the 51% no progression rate calculated from the subjects who took NSAIDs will be used for GP2017 (adalimumab biosimilar). Assuming 80% of subjects will complete the 2-year study treatment period and provide both baseline and Week 104 evaluable radiographic films with a 66% no progression rate at Week 104 and assuming subjects who discontinue study treatment will have a 51% no progression rate at Week 104, a new no progression rate of 63% for secukinumab was calculated using the definition of the estimand. Therefore, a no progression rate of 63% for secukinumab and 51% for GP2017 were used as assumptions to calculate the sample size using a two-group Chi-square test of equal proportion (nQuery Advisor 7.0) with approximately 73% power at  $\alpha=0.025$ . And the power to reject at least one hypotheses using the Hochberg procedure is 88%.

Analysis of an unpublished Phase III study showed a change from baseline in mSASSS at Week 104 with a mean of 0.52 and standard deviation of 2.5 for secukinumab subjects. With a sample size of 279 subjects in each treatment group, a treatment difference of 0.58 (i.e., assuming GP2017 has a mean of 1.1 and the same standard deviation) yields approximately 68% power at  $\alpha = 0.025$ .

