#### **Missing post-baseline value**

1. A missing value for a post-baseline VU will be replaced with the nearest value available. For Week 52: if both baseline VU and Week 104 VU are available, the baseline VU value will be used.
2. The mean spinal segment's progression score (either cervical or lumbar) per subject will be calculated.
3. The mean spinal segment's progression score will be added to the imputed post-baseline value in #1.

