**Table 5-3 Analysis visit windows**

Analysis Visit	Target Day	Analysis Visit Window	Group 1	Group 2	Group 3	Group 4	Group 5
Baseline	1	≤ 1	≤ 1	≤ 1	≤ 1	≤ 30	≤ 7
Week 4	29	2-57	2-57				
Week 8	57						
Week 12	85	58-99	58-99				
Week 16	113	100-141	100-141	2-239	2-239		54-173
Week 20	141						
Week 24	169	142-225	142-225				
Week 28	197						
Week 32	225						
Week 36	253						
Week 40	281	226-323	226-323				
Week 44	309						
Week 48	337						
Week 52	365	324-407	324-407	240-547	240-407	276-455	276-455
Week 56	393						

Analysis Visit	Target Day	Analysis Visit Window	Group 1	Group 2	Group 3	Group 4	Group 5
Week 60	421						
Week 64	449	408-491	408-491		408-491		
Week 68	477						
Week 72	505						
Week 76	533	492-589	492-589		492-589		
Week 80	561						
Week 84	589						
Week 88	617						
Week 92	645	590-687	590-687		590-687		
Week 96	673						
Week 100	701						
Week 104	729	688-785	688-785	548-785	688-785	640-849	640-819

Group 1: Subject's global assessment of disease activity (VAS), Subject's assessment of back pain intensity (VAS), BASFI, BASDAI, [REDACTED], hsCRP, vital signs, hematology, blood chemistry, urinalysis

Group 3: Weight

Group 4: Lipids, X-ray

Group 5: MRI

The following rules are used to determine the window for an applicable visit post baseline: "Lower limit" = "upper limit of prior applicable visit" + 1. "Upper limit" = "target day of current visit" + integer part of ("target day of next applicable visit" - "target day of current visit")/2. Lower limit of the first applicable visit is always Day 2.

The mapping described above applies to all visits (not just scheduled visits). Repeat and/or unscheduled visits (which will be numbered in the database according to new NCDS standards) will be mapped for analysis purposes in the same way as scheduled visits. This leaves the possibility, then, for multiple measurements within an analysis window. The following conventions will be used to determine the appropriate measurement to be summarized in the event of multiple measurements within a visit window.

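### SAP 2.5.3: each donor's slope covariate is the Week 104 change itself, so the primary imputation mostly extrapolates the recipient's earlier film and loses most of what donors show about progression after stopping treatment

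*SAP*

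**What the plan says.** The primary outcome is binary: no progression means a Week 104 change in mSASSS of at most 0.5, under an estimand that applies regardless of adherence (SAP 2.5.1). For subjects who discontinued and lack Week 104 data, SAP 2.5.3 specifies a retrieved-dropout model: "A logistic regression model will be fitted to the Week 104 X-ray data for the retrieved dropout patients", with terms for treatment, baseline mSASSS and a post-baseline slope. The slope is defined thus: "The post-baseline slope is defined as the last available post-baseline change in mSASSS score divided by study day on which the X-ray was taken". Its justification is literature reporting linear progression in patients treated with TNF inhibitors.

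Three other parts of the plan use the same slope:

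- the run for Week 104 scores missing because of uninterpretable locations, which is "based on the observed data of all subjects who provided Week 104 data";
- both fallback models for sparse donors, which drop treatment but keep the slope;
- the no-new-syndesmophyte endpoint (H5/H6): "For absence of new syndesmophytes at Week 104, the handling of missing data will be the same as the primary endpoint".

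Only subjects with no post-baseline value are imputed without the slope.

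Protocol 9.4.3 names the recipient's own data as Baseline and Week 52. In SAP Table 5-3 ("Group 4: Lipids, X-ray") the X-ray windows are Days 276-455 for Week 52 and Days 640-849 for Week 104. No spinal film is scheduled after Week 104.

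**The concern.** A donor has a Week 104 film by definition. With no cut-off, the donor's last available change is the Week 104 change, so the model regresses an outcome on its own value before it was cut at 0.5. A recipient has no Week 104 value, so the same coefficient is applied to an earlier film.

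The retrieved-dropout approach is there to carry outcomes seen after stopping treatment over to the subjects whose outcomes are missing. When the slope explains the donors' outcomes almost perfectly, the treatment terms have little left to learn. The imputation then becomes close to a rule that extends the recipient's own earlier film.

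This matters for the treatment contrast if progression changes after discontinuation in one arm more than another. The plan's sample size section assumes such a change: secukinumab goes from 66% on treatment to the figure used for discontinuers ("assuming subjects who discontinue study treatment will have a 51% no progression rate at Week 104"), while GP2017 is 51% throughout.

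**Working it through.** **1. Planning figures.** 0.8 × 66% + 0.2 × 51% = 52.8% + 10.2% = 63.0%, as stated. With 279 per arm, 63% versus 51% and α = 0.025, the chi-square power is 73.4% (stated 73%). Power to reject at least one hypothesis by Hochberg is 87.9% by simulation (stated 88%). The plan's inputs are therefore read correctly.

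**2. Separation among donors.** Scores are the average of three readers (SAP 5.1), so changes fall on a grid of 1/3 unless vertebral units are filled in.

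- Largest slope of a non-progressor: (1/3)/640 = 0.00052 per day.
- Smallest slope of a progressor: (2/3)/849 = 0.00079 per day.

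On the grid the classes cannot overlap, even at the window edges. Off-grid values arise from segment-mean filling ("The mean spinal segment's progression score will be added to the imputed post-baseline value in #1"). The classes can then overlap for changes between 0.5 × 640/849 = 0.38 and 0.5 × 849/640 = 0.66. With 20% of scores off the grid, separation was still complete in 99.6% of 2,000 simulated sets of 60 donors.

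**3. Consequence for a recipient.** The fitted cut lies near 0.5/729 = 0.00069 per day. A Week 52 change of +1/3 gives (1/3)/365 = 0.00091 (0.00073 to 0.00121 across the window), on the progression side. A change of 0 falls on the other side. One reader scoring one corner one grade higher moves the average by 1/3, enough to change sides.

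**4. How much donor information gets through.** A simulation of the 2.5.3 model used its priors, 10, 20 or 40 donors and 28 recipients per arm, and a Week 52 film for every recipient. The standardised square root of baseline was used. Progression after stopping was varied while the Week 52 data were held fixed.

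- The share of a true shift in the recipients' rate that reached the imputations was 6-23% as written, and 77-97% with the donor slope taken from Week 52.
- With 20 donors per arm, as the true recipient rate fell from about 65% to 26%, the imputed rate moved from 55% to 51% as written and from 63% to 28% with the earlier film.
- A true gap of 20 to 24 points between arms' dropouts was imputed as 4 to 7 as written and 19 to 22 with the earlier film.
- The priors in SAP 5.4.3.2 (variances 2 and 3, where 2.5.3 has SDs 2 and 3) gave shares of 12% and 79%.

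**5. Effect on the trial.** Assumptions: 279 per arm; 20 donors and 36 recipients per arm (20 + 36 = 56, which is 20% of 279); recipients' film taken before any shift; error SD of a change score 0.8 (range 0.4 to 1.13); 100 imputations with Rubin's rules. Bias is in percentage points, positive favouring secukinumab. The second column uses the unadjusted difference. The third uses the planned baseline-adjusted logistic regression with marginal standardisation, where run.

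| Shift after discontinuation | Bias as written, unadjusted | Bias as written, planned estimator |
|---|---|---|
| Plan's own (secukinumab 66% to 51%, true difference 12) | +1.1 (range +1.0 to +1.3) | +1.1 |
| 0.6 units, secukinumab only | +2.6 (+1.9 to +4.7) | +2.4 |
| 0.6 units, GP2017 only | -3.4 | not run |
| None | -0.5 | -0.6 |
| Equal in all arms | -0.1 | not run |

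Under the plan's own shift:

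- Imputed no-progression in the secukinumab arms is about 6 points too high as written, and within 1 point with the fix.
- With the fix the bias is -0.2 to +0.3 unadjusted and +0.1 with the planned estimator.
- If 12 of the 36 recipients have no film, the bias as written is +0.6.
- Rejection of a single comparison at two-sided 5% is 88% versus 74% with the fix (87% versus 74%, planned estimator).
- Coverage of the 95% interval is 94% versus 95%.
- The SE is 0.0424 versus 0.0465, and the mean slope coefficient about -9.0 versus -1.4.

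Under the 0.6-unit secukinumab-only shift, coverage is 92% versus 96%. If that shift makes the overall effect exactly null, false rejection in favour of secukinumab is 9.2% versus 3.1% (nominal 2.5%).

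**6. Reading the rejection rates.** By normal approximation, complete data at 63% versus 51% give 82% at two-sided 5%. For an unbiased difference, Φ(0.12/0.0424 − 1.96) = 81% and Φ(0.12/0.0465 − 1.96) = 73%. Adding the bias, Φ(0.131/0.0424 − 1.96) = 87%. So about half of the gap comes from the smaller SE and the rest from bias. As written, the analysis rejects more often than complete data would, with 36/279 = 13% of outcomes imputed.

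**The case against.** The strongest reply is that a slope from before Week 104 was intended. Protocol 9.4.3 mentions Baseline and Week 52, and SAP Section 4 declares no change from the protocol. That may be so, but the protocol sentence concerns the recipient's data and does not settle the donors' covariate. Neither 2.5.3 nor the code in 5.4.3.2 excludes the Week 104 film, so a programmer following the text would build the defect. Linear progression does not rescue it either: the cited evidence is from treated patients, and linearity gives no reason to put the outcome film among the predictors.

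The second reply is size, and much of it stands:

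- Under the plan's own shift the bias is 1.1/4.24 = 0.26 of an SE, and no loss of coverage is shown.
- The 0.6-unit shift exceeds the 0.58-unit whole-trial difference assumed in the sample size section, so it is a stress test and not an expectation.
- Taking every recipient's film before the shift is unfavourable. A subject who stopped early and left later may have an off-treatment film.
- Part of the gap in rejection rates is the SE. The smaller SE is nevertheless part of the defect, because extrapolated outcomes are treated as nearly known.

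Third, the binary tipping-point analysis does not use the slope and partly mitigates. It does not correct the primary estimate, and the unused models offered as sensitivity analyses keep the slope. The effect on H5/H6 was not simulated. There the outcome is not a direct function of the slope, but the donor covariate still contains the Week 104 film and is not comparable with the recipient's.

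**Conclusion.** The plan is wrong as written, and this must be fixed because it sits in the confirmatory primary analysis. That the donor covariate contains the outcome follows from the SAP's text alone. Near-complete separation follows from its score grid and windows, apart from off-grid filled values.

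The size depends on the assumed numbers of donors, recipients and films, the progression distribution and reader error. Under the plan's own discontinuation assumption it is about +1.1 points towards secukinumab, with rejection 13 to 14 points higher than under a comparable covariate. The direction depends on which arm changes after stopping, so the error cannot be presumed conservative. With no shift or an equal one it is small, and recipients with no post-baseline film are not affected.

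**What to change.** In SAP 2.5.3, define the post-baseline slope as the change at the last film before the Week 104 analysis window (before Day 640) divided by its study day. Apply this to donors and recipients alike, in both MCMC runs and both fallbacks, and standardise on one common mean and SD. Use the already specified no-slope model for subjects without such a film, and carry the definition over to H5/H6.

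The cost is one sentence and a re-derived covariate, with no new data. The SE rises from 0.0424 to 0.0465 in the simulation, which reflects the uncertainty about the missing outcomes. Donors without an earlier film would inform only the no-slope model, so the SAP should say which donors count towards the threshold of 8 for the fallback. Comparability will not be perfect: films are requested at early discontinuation ("unless the last X-ray and/or MRI was taken within 12 weeks prior to discontinuation", Protocol Section 6), so some recipients' last film may fall between the Week 52 window and Day 640, while donors mostly contribute Week 52. Dividing by study day allows for this only as far as progression is linear.

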For the datasets generated with the PROC MCMC routine, the same analysis as described in this section will be performed. PROC MCMC will be run twice with 100000 iterations, a thinning of 1000, and burn-in of 10000 in order to obtain 200 partially completed datasets. 100 datasets will have imputed data for subjects who discontinued the study, and the other 100 datasets will have imputed data for subjects with missing data for other reasons (e.g., due to an incomplete number of interpretable locations). The two sets of 100 partially completed datasets will be patched together matching their iteration number. That is, the datasets corresponding to the  $i$ -th iteration of the first 100 datasets will be merged with the datasets corresponding to the  $i$ -th iteration of the second 100 datasets. The SAS code below outlines a template for the procedure:

```
PROC MCMC data= seed=4572340 nbi=10000 nmc=100000 thin=1000
missing=CCMODEL;
    parms beta1 beta2 beta3 beta4 beta5;
    prior beta1 beta2 beta3 ~ normal(0,var=2);
    prior beta4 beta5 ~ normal(0,var=3);
    pi = logistic(beta1 * trt_GP2017 + beta2 * trt_SEC150 + beta3 * trt_SEC300 + beta4 *
sqrt(base_stand) + beta5 * slope_stand);
    model y ~ binary(pi);
    preddist outpred=;
run;
```

Analogous codes will be used to impute the missing data due to other reasons (other than study discontinuation) as well as the change from baseline in mSASSS at Week 104 (secondary endpoint).

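### The primary imputation code takes the square root of an already standardized baseline mSASSS, and the SAP gives two different prior sets for the same coefficients

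*SAP*

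**What the plan says.** SAP 2.5.3 imputes missing Week 104 no-progression status with a Bayesian logistic model in PROC MCMC. On scaling it says: "The covariates of baseline mSASSS and slope will be standardized to have a mean of 0 and standard deviation of 1 before model fitting". The linear predictor then has three treatment indicators plus "beta4*sqrt(base_stand) + beta5*slope_stand". The legend describes the baseline term as "square root of the baseline mSASSS (standardized", with the bracket closing there.

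The same `sqrt(base_stand)` appears in two more places:

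- the 2.5.3 fallback for sparse retrieved-dropout data, of which the SAP says "In this case imputations will be performed based on a model without treatment as a covariate";
- the code in 5.4.3.2, introduced by "The SAS code below outlines a template for the procedure".

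The priors in 2.5.3 are given as standard deviations: "prior beta1 ~ normal(0,sd=2"), the same for beta2 and beta3, and `sd=3` for beta4 and beta5. The 5.4.3.2 code gives `var=2` for beta1 to beta3 and `var=3` for beta4 and beta5.

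For comparison, the 2.6.3 model for mSASSS change uses a ready-made variable, `sq_base_stand`, with the legend "square root of baseline mSASSS (standardized", and states its normal priors by standard deviation, for example "prior beta1 ~ normal(0,sd=100").

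**The concern.** There are two separate defects in the specification of one model.

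First, the order of operations. The text standardizes and the code then takes a root, whereas the legend suggests taking the root and then standardizing. Only the second order gives every subject a covariate value.

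Second, the priors. The same coefficients in the same model have two written priors that differ in variance by a factor of 2 or 3.

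Whoever programs the primary imputation must therefore depart from the written code to get a computable covariate and must also pick one of the two priors. Two competent programmers could produce different primary results from the same SAP. Section 2.6.3 handles missing data for absence of new syndesmophytes in the same way as the primary endpoint, so H5 and H6 inherit the problem.

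**Working it through.** The SAP gives no figure that depends on this point, so there is none to reproduce.

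**1. Square root.** Let z = (x − mean)/SD, where x is baseline mSASSS. Then z < 0 whenever x is below the mean, and √z is not a real number. This needs no distributional assumption. The documents give no baseline distribution, so the share affected is an assumption: 50% if symmetric, 63% for an exponential shape, and 68% to 73% for gamma shapes of 0.5 and 0.3. In the reverse order, √x is defined over the whole mSASSS range of 0 to 72, and standardizing it leaves no subject undefined.

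**2. Prior conversion.** SD = √variance.

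| Coefficients | 2.5.3 | 5.4.3.2 | Variance ratio | 95% prior range (logits) |
|---|---|---|---|---|
| beta1–beta3 (arms) | SD 2, variance 4 | variance 2, SD 1.41 | 2 | ±3.92 vs ±2.77 |
| beta4–beta5 (baseline, slope) | SD 3, variance 9 | variance 3, SD 1.73 | 3 | ±5.88 vs ±3.39 |

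**3. Effect on one arm, intercept only.** With n retrieved dropouts and k non-progressors, the posterior for the arm intercept b is proportional to Binomial(k; n, logistic(b)) × Normal(b; 0, SD²). The imputed rate is the posterior mean of logistic(b).

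Inputs from the documents are 279 per arm and 80% completion (sample size sections). That gives 0.20 × 279 ≈ 56 non-completers per arm. The number retrieved is an assumption; 8 is the smallest count at which 2.5.3 keeps treatment in the model. The arm rate moves by the shift in imputed rate × (56 − n)/279. For n = 8 the multiplier is 48/279 = 0.172; for n = 30 it is 26/279 = 0.093.

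| k/n | Imputed rate, sd=2 | Imputed rate, var=2 | Shift (points) | Shift in arm rate (points) |
|---|---|---|---|---|
| 4/8 | 50.0% | 50.0% | 0 | 0 |
| 5/8 | 60.9% | 59.8% | 1.2 | 0.2 |
| 7/8 | 82.0% | 78.4% | 3.6 | 0.6 |
| 8/8 | 91.2% | 86.7% | 4.5 | 0.8 |
| 19/30 | 62.9% | 62.5% | 0.4 | 0.04 |

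Shifts are taken before rounding.

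The bottom two rows for n = 8 are unlikely. At the planning rate of 51% for discontinuers, P(7 or 8 of 8) = 8 × 0.51⁷ × 0.49 + 0.51⁸ ≈ 4%, and P(8 of 8) = 0.51⁸ ≈ 0.5%. Averaged over all k at 51%, the expected absolute shift in the arm rate is 0.22 points with 8 retrieved, 0.10 with 14 and 0.02 with 30.

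**4. Effect on the treatment difference, all five coefficients.** Data were simulated (250 datasets per setting) and fitted under both prior sets with the covariate as a standardized square root. Assumptions: baseline gamma with shape 0.6 and mean 16; 51% no progression at average covariates; logit slopes (−0.7, −0.7) or (−1.0, −1.5).

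| Retrieved per arm | Median shift in difference (points) | 95th percentile |
|---|---|---|
| 8 | 0.3 | 0.8 to 0.9 (maximum 1.7) |
| 14 | 0.15 | 0.4 to 0.5 |
| 30 | 0.04 | 0.1 |

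The planned difference is 63% − 51% = 12 points.

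**The case against.** The strongest reply is that the first defect is a notation slip whose intent can be recovered. The legend for slope also puts the word standardized after the whole derived quantity, and 2.6.3 uses almost the same legend for a variable that plainly is a standardized square root. The scaling sentence can be stretched to mean the covariates derived from baseline and slope. A failure affecting perhaps half the subjects or more would also be noticed in programming. All of this makes the intended covariate fairly clear. It does not make the written code right: the expression occurs in all three places, so the fallback does not avoid it.

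On the priors, it can be said that 2.5.3 governs because 5.4.3.2 calls its code a template. That is a good reason for choosing `sd=`, but the SAP does not state that order of precedence, and the template has specific numeric priors alongside its seed, burn-in, iterations and thinning. One could argue the other way that `var=` is newer, since the document history dates the template code to Amendment 3. The same amendment also corrected the model notation in 2.5.3, which weakens that argument.

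The objection on size stands. The shifts are small, the largest ones are tail cases, and the binary tipping point analysis runs through every split of the missing responses, so completed counts under either prior fall within its grid (tested there by chi-square, not by the primary model).

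**Conclusion.** Both defects are real and can be read directly from the SAP. The baseline term is undefined for every below-mean subject if the code is run literally, and for no subject under the legend's reading. The prior conflict is literal and needs no interpretation.

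The consequence is limited. It is confined to imputed subjects: observed Week 104 outcomes are unaffected, and the analysis model in 2.5.2 uses untransformed baseline mSASSS. The prior choice typically moves the treatment difference by a few tenths of a point when retrieved dropouts are scarce and by almost nothing when they are plentiful. Those sizes rest on 80% completion, the assumed retrieved counts and the simulated covariate effects. This should be fixed because a primary imputation needs one executable specification before lock, not because it is likely to reverse the result.

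**What to change.** 1. Define the baseline covariate as the square root of raw baseline mSASSS, then standardized. Amend the scaling sentence in 2.5.3 accordingly, and replace `sqrt(base_stand)` with one precomputed variable (for example `base_sqrt_stand`) in the 2.5.3 main code, the 2.5.3 fallback code and the 5.4.3.2 template.
2. State one prior set in both sections: sd=2 for the treatment coefficients and sd=3 for baseline and slope, correcting the `var=` entries in 5.4.3.2. Section 2.5.3 specifies the primary analysis, 5.4.3.2 is a template, and 2.6.3 also states its normal priors by SD. If the sponsor intended the variances, writing them in both places would equally remove the conflict.
3. As a useful addition, say which subjects supply the mean and SD for standardizing, because that choice sets the scale on which the priors act.

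The cost is a SAP wording and code correction before lock.
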